### Establish the efficacy of online perceptual training for children with RSE and atypical perception

#### OBJECTIVE:

Evaluate whether online perceptual training improves perception and production of /r/ in children with Residual Speech Errors (RSE) who have atypical perceptual acuity, as identified by our lab-based classification norms.

#### Participants

- **Sample:** 10 children with RSE affecting /r/
- **Age range:** 9;0–15;11 years, native English speakers

#### Eligibility

##### Residual Speech Errors (RSE):

Must have persistent speech errors specifically affecting the English rhotic /r/ sound.

- **Perceptual Classification:**  
Must be classified as having *atypical perception* based on a laboratory-developed classification model applied to standardized perception tasks.
- **Language Background:**  
Native speakers of English.
- **Cognitive and Language Proficiency:**  
Must demonstrate adequate nonverbal cognitive and language skills as assessed by standardized tests, including:
  - **Goldman-Fristoe Test of Articulation—Third Edition (GFTA-3):** Assesses articulation of speech sounds.
  - **Clinical Evaluation of Language Fundamentals—Fifth Edition (CELF-5), Recalling Sentences (RS) and Formulated Sentences (FS) subtests:** Evaluates expressive and receptive language functioning, focusing on sentence recall and formulation.
  - **LinguiSystems Articulation Test (LAT):** Measures production of specific speech sounds.

- **Sentence Repetition Task (SRT):** Assesses verbal memory and grammatical processing through sentence repetition.

- **Hearing Screening:**

Must pass an online pure-tone hearing screening at frequencies 1000 Hz, 2000 Hz, and 6000 Hz, at 30 dB intensity.

- **Medical History:**

Must not have a history of major neurobehavioral disorders or developmental disabilities.

- **DESIGN AND PROCEDURES**

- **Design:** Multiple-baseline across-subjects design; participants randomly assigned to varying baseline durations (4–10 sessions).
- **Phases:**
  - **Baseline:** Perception and production of /r/ are probed repeatedly without intervention.
  - **Treatment:** All participants complete 12 sessions of online perceptual training (3x/week, 4 weeks).
  - **Maintenance:** Post-treatment, perception and production are monitored for 3 sessions; no further training.

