Online assessment and enhancement of auditory perception for speech sound errors

Protocol NCT04858035

Document generated 03/17/2021

4.3 Statistical Design and Power: Study 3

In the proposed multiple-baseline across-subjects design with randomization, participants' progress will be tracked continuously across baseline and treatment phases using percent accuracy on the two perceptual tasks described in the main proposal. Accuracy in baseline versus treatment phases of the study will be compared using Koehler and Levin's randomization test [101] as implemented in the R package SCRT [102], with visual inspection as a secondary analysis. Visual inspection will compare the baseline and treatment phases for each participant to identify any differences in level, slope, and variability. In addition, trends will be compared across participants to assess whether changes in performance are temporally linked to the introduction of treatment, to evaluate the immediacy of any such changes, and to examine consistency across participants [119]. The SCRT algorithm will evaluate whether the observed difference in accuracy between baseline and treatment phases is unlikely to occur ($p < .05$) relative to the distribution of differences obtained when a null effect is assumed and the labels "baseline" and "treatment" are randomly assigned in all permutations permitted by the specified multiple-baseline design. If there is a statistically significant effect of treatment, the observed difference will be extreme relative to this distribution. In particular, for a p-value of .05, we would expect to see no more than 5% of estimates from the simulated distribution with absolute values equal to or greater than our observed estimate. In addition to the randomization test, we will calculate standardized effect sizes for each participant (Busk & Serlin's d_2 [103]), comparing their performance in the pre-treatment baseline versus post-treatment maintenance phase and dividing by the pooled standard deviation. These will be used to evaluate, at both individual and group levels, whether the effect of treatment on perceptual accuracy exceeds 1.0, a benchmark commonly accepted to represent the minimum clinically significant effect size [99]. The same effect size measure will be used to compare production accuracy in the first three baseline sessions versus the three post-treatment maintenance phases, to test whether gains in perception transfer to production.

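### Outside speech therapy for /r/ is neither excluded nor recorded, and the only production analysis is a before-after d_2 that would count its gains as transfer from perceptual training

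*Protocol*

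**What the plan says.** The Protocol's Objective names both perception and production of /r/. The Participants and Eligibility sections set the entry rules:

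- age 9;0 to 15;11 and native English
- the target error: "Must have persistent speech errors specifically affecting the English rhotic /r/ sound"
- atypical perception by the laboratory's classification model
- standardized articulation, language and sentence-repetition tests
- an online hearing screening
- medical history: "Must not have a history of major neurobehavioral disorders or developmental disabilities"

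No rule concerns current or planned speech therapy. Design and Procedures describes baseline as probing with no intervention and maintenance as monitoring with no further training. Both statements describe the study's own phases. Perception Training adds a weekly clinician-attended session, in the treatment phase only, to check engagement.

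SAP section 4.3 gives the two outcomes different analyses. Progress is "tracked continuously across baseline and treatment phases using percent accuracy on the two perceptual tasks described in the main proposal", and the randomization test compares baseline with treatment on that accuracy. For production, d_2 has this task: "compare production accuracy in the first three baseline sessions versus the three post-treatment maintenance phases, to test whether gains in perception transfer to production". No other production analysis is specified.

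**The concern.** Older children with a persistent /r/ error are a group in whom outside /r/ therapy is foreseeable. A site that followed the Eligibility list exactly could enrol a child who has such therapy throughout participation, and no one would have a record of it.

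The production analysis cannot separate the two sources of change. It sets each child's earliest sessions against the last ones and makes no use of the randomized stagger in start times. Whatever moves production in between is read as transfer. The blinded listeners do not help, because therapy that works produces real improvement, and a blinded rater scores it correctly. A gain from therapy would push the result towards a positive finding on a stated objective. If therapy status was never collected, it cannot be recovered at analysis.

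**Working it through.** **The plan's own figure.** The plan gives none on this point. The 80% power in SAP 4.3 concerns the randomization test and is unaffected.

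**Step 1: distance between the compared sessions.** Inputs from Design and Procedures: baseline B = 4 to 10 sessions, 12 treatment sessions, 3 maintenance sessions. The first three baseline sessions have their midpoint at session 2, and the maintenance sessions at session B + 12 + 2.

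- Gap = (B + 14) − 2 = B + 12, which is 16 sessions for B = 4 and 22 for B = 10.
- The Protocol gives a pace of 3 per week for treatment only. Assuming it for all phases, the gap is 16/3 = 5.3 weeks to 22/3 = 7.3 weeks.

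A longer baseline widens the gap, because only its first three sessions are used.

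**Step 2: outside gain that shifts production by 1.0 SD with no training effect.** 1.0/5.33 = 0.19 SD per week for B = 4, and 1.0/7.33 = 0.14 SD per week for B = 10.

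**Step 3: effect on d_2.** Simulated series had autocorrelation 0.25 (the SAP's value for its power calculation), within-child SD 1, zero training effect and a linear outside gain. d_2 = (mean of 3 maintenance sessions − mean of first 3 baseline sessions) / pooled SD.

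| Assumed outside gain (SD per week) | Median d_2, B = 4 to B = 10 | P(d_2 > 1), B = 4 to B = 10 |
|---|---|---|
| 0 | 0 | about 0.20 |
| 0.1 | 0.63 to 0.86 | 0.38 to 0.45 |
| 0.2 | 1.29 to 1.74 | 0.59 to 0.73 |

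The first row matters as well. With only three sessions on each side, d_2 exceeds 1 in about one child in five by noise alone.

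**Step 4: group mean.** Each child carries one tenth of it. If 2, 4 or 6 of 10 children each gained an assumed 1.0 SD from therapy, the mean shift would be 0.2, 0.4 or 0.6 SD. If their therapy gain were zero, it would be 0.

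**Step 5: does the randomization test share the problem?** Simulation with n = 10, baselines of 4 to 10, a common series of 22 observations (10 + 12, assumed), autocorrelation 0.25, zero training effect, one-sided test at 0.05, 1000 replicates:

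| Outside therapy | Rejection rate |
|---|---|
| None | 0.061 |
| Steady gain of 0.2 SD per week | 0.063 |
| 1.0 SD step at a random session, all children | 0.046 |
| Same step, 6 of 10 children | 0.039 |

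None of the therapy scenarios shows inflation beyond simulation error. Therapy whose timing does not depend on the assigned start is present alike in the observed and the re-randomized arrangements, so the test keeps its size.

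**The case against.** The strongest reply is that the root fault is the analysis. An uncontrolled before-after d_2 also absorbs maturation and repeated probing, and excluding therapy leaves those in place. This stands in part: applying the randomization test to production would protect it against outside therapy unrelated to the start. It would not tell anyone which children had therapy, and the d_2 would still be reported.

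A reader might go further and infer that outside therapy spoils production under any statistic, or that it biases the primary perception result. The documents do not support either. Baseline length is randomized, and step 5 shows the test holding its size. Bias would need therapy timing that follows the assigned start, and nothing in the documents suggests that. For perception, only the supplementary d_2 is exposed.

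Three further points are fair:

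- The word persistent may describe children who gain little from ongoing therapy, so near-zero gain belongs in the range. It does. The Eligibility section does not, however, define persistence by therapy history.
- The 1.0 benchmark is stated for perception ("whether the effect of treatment on perceptual accuracy exceeds 1.0, a benchmark commonly accepted to represent the minimum clinically significant effect size"). For production, the SAP carries over the measure without restating the threshold.
- The Protocol is brief, and the SAP refers to a main proposal that is not available here. A therapy rule may exist there, but it is absent from the eligibility list a site would follow.

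**Conclusion.** The concern holds for the production conclusion. As written, the plan allows concurrent /r/ therapy, does not record it, and tests transfer with a contrast that cannot separate its effect from that of the training.

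The size of the bias is not known. The range in step 3, a median d_2 from 0 to about 1.3 to 1.7 in a child receiving therapy, rests on assumed gains of 0 to 0.2 SD per week, all sessions at 3 per week, autocorrelation 0.25 and a linear gain. It shows what is possible and should not be read as an estimate of what will occur.

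The primary perception test is not called into question, on the assumptions of step 5: therapy timing unrelated to the randomized start, and a common series length. The plan should be changed, because the missing information cannot be recovered later and is cheap to collect.

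**What to change.** 1. **Protocol, Eligibility.** Add a criterion that the child is not receiving, and is not scheduled to begin, speech therapy directed at /r/ between the first baseline and the last maintenance session, by parent report at screening. No child is asked to stop care; the rule concerns only who is enrolled.
2. **Protocol, Design and Procedures.** Ask about outside /r/ therapy and log it with dates in baseline, treatment and maintenance. The existing weekly clinician contact covers treatment only, so the other two phases need their own short parent question.
3. **SAP 4.3.** Keep the production result in all children. Add a pre-specified sensitivity result that excludes children with logged /r/ therapy, and word the transfer conclusion according to both.

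Applying the randomization test to production as well would add protection against outside gains unrelated to the assigned start.

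The cost is one eligibility sentence, one screening question, a short parent question per phase or week, and a short SAP addition. Recruitment of 10 children would be somewhat slower, and the sensitivity result may rest on fewer than 10, which is why the all-children result stays.

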### **Assessment Measures:**

- **Perception:**
  - Online identification and category goodness judgment tasks
  - For ongoing assessment, 75 items are randomly drawn (with proper balance and difficulty stratification) to avoid item memorization
- **Production:**
  - Standardized word probes
  - Perceptual ratings are obtained from blinded online listeners

### **Perception Training (Treatment Phase)**

- **12 sessions** (30 minutes each, over 4 weeks; mostly self-administered online)

- **Task 1:** Focused perceptual training in a specific /r/ context with feedback; difficulty increases with improved accuracy.
- **Task 2:** Identification of items along a synthetic rake-wake continuum with feedback based on typical listener norms.
- **Task 3:** Broad perceptual training with a randomized set of items across all /r/ contexts and difficulties, with feedback.
- **Clinician Monitoring:** A study clinician virtually attends one session per participant each week to ensure engagement.

### **Summary Statement:**

This study will rigorously test whether online perceptual training leads to measurable improvements in both perception and production of /r/ in children with RSE and atypical perception, using a robust, randomized multiple-baseline design and blinded standardized outcome measures.

Online assessment and enhancement of auditory perception for speech sound errors

Protocol NCT04858035

Document generated 03/17/2021

4.3 Statistical Design and Power: Study 3

In the proposed multiple-baseline across-subjects design with randomization, participants' progress will be tracked continuously across baseline and treatment phases using percent accuracy on the two perceptual tasks described in the main proposal. Accuracy in baseline versus treatment phases of the study will be compared using Koehler and Levin's randomization test [101] as implemented in the R package SCRT [102], with visual inspection as a secondary analysis. Visual inspection will compare the baseline and treatment phases for each participant to identify any differences in level, slope, and variability. In addition, trends will be compared across participants to assess whether changes in performance are temporally linked to the introduction of treatment, to evaluate the immediacy of any such changes, and to examine consistency across participants [119]. The SCRT algorithm will evaluate whether the observed difference in accuracy between baseline and treatment phases is unlikely to occur ($p < .05$) relative to the distribution of differences obtained when a null effect is assumed and the labels "baseline" and "treatment" are randomly assigned in all permutations permitted by the specified multiple-baseline design. If there is a statistically significant effect of treatment, the observed difference will be extreme relative to this distribution. In particular, for a p-value of .05, we would expect to see no more than 5% of estimates from the simulated distribution with absolute values equal to or greater than our observed estimate. In addition to the randomization test, we will calculate standardized effect sizes for each participant (Busk & Serlin's d_2 [103]), comparing their performance in the pre-treatment baseline versus post-treatment maintenance phase and dividing by the pooled standard deviation. These will be used to evaluate, at both individual and group levels, whether the effect of treatment on perceptual accuracy exceeds 1.0, a benchmark commonly accepted to represent the minimum clinically significant effect size [99]. The same effect size measure will be used to compare production accuracy in the first three baseline sessions versus the three post-treatment maintenance phases, to test whether gains in perception transfer to production.

Power for the randomization test was estimated using the method proposed by Bouwmeester & Jongerling [111] and their associated app built with the Shiny package [112] in R [89]. Per their research, power in a multiple-baseline across-subjects randomization study is influenced by (a) the number of participants, (b) the within-subject effect size, (c) the number of observations per phase, (d) the level of autocorrelation between observations within participants, and (e) the range of possible start points for the intervention, and whether this range overlaps across participants. Power of 80% was observed in a calculation assuming (a) $n = 10$ participants, (b) a within-subject effect size of 1.0 (which we treat as the minimum clinically relevant difference as in [99]), (c) 15 observations per participant, (d) autocorrelation of .25, based on pilot data, (e) at least 4 possible start points, with overlapping start points across participants, and (f) additional characteristics of the baseline phase including unequal numbers of observations between baseline and intervention phases, correlation between scores across baseline and intervention phases, and greater variance in the intervention than the baseline phase.

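### Do two perceptual tasks without a stated decision rule leave the SAP's .05 and 80% power without meaning?

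*SAP*

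**What the plan says.** SAP section 4.3 follows each child through baseline and treatment "using percent accuracy on the two perceptual tasks described in the main proposal". The Protocol, under Assessment Measures, names the perception measures: "Online identification and category goodness judgment tasks".

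The SAP then sets out a Koehler-Levin randomization test, run in a named R package, over the assignments that the multiple-baseline design allows. The criterion is that the observed baseline-to-treatment difference "is unlikely to occur ($p < .05$) relative to the distribution of differences" expected under no effect. It is two-sided, because it counts permuted estimates "with absolute values equal to or greater than our observed estimate".

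The power paragraph concerns this randomization test: "Power of 80% was observed in a calculation assuming" ten participants, a within-subject effect of 1.0, 15 observations each and autocorrelation .25. Separately, a standardized effect size (d_2) is calculated for each child, to judge "whether the effect of treatment on perceptual accuracy exceeds 1.0".

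Neither document says how results on two tasks become one statement about perception. No primary task, combined score, either-or-both rule or multiplicity adjustment is given. For the tasks themselves the SAP refers to a main proposal that is not among the documents.

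**The concern.** The study asks one question about perception but has two measures of it. When the step from two results to one conclusion is not fixed, the error rate and power of that conclusion depend on a choice that could be made after the data are seen. If a significant result on either task were enough, the two-sided error would exceed 5%. If both were needed, power would fall below 80%.

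The tasks might also respond differently. One training component is "Identification of items along a synthetic rake-wake continuum with feedback based on typical listener norms", which resembles the identification outcome more closely than the goodness judgment. If only one task moved, the same data could support opposite conclusions under different rules. On this view the .05 and the 80% belong to no defined test. The d_2 benchmark of 1.0 has a similar ambiguity, since two tasks give two values per child.

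**Working it through.** **Inputs.** From SAP 4.3: two-sided alpha .05 and power 80%, taken here as true for each task. Assumed: correlation r between the two test statistics of 0, .5, .9 and .99, because the documents give no value. The two statistics are treated as bivariate normal.

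**1. Can the 80% belong to one test?** A simplified simulation of the randomization test was run for one outcome (independent random start points, AR(1) errors, n = 10, effect 1.0, 15 observations, autocorrelation .25). With equal variances it gave 81% power when start points were spread over sessions 4 to 10, and 66% with four adjacent start points (4 to 7). With a treatment-to-baseline SD ratio of 1.25 to 1.5, power fell to 73% to 65% (spread) and 57% to 50% (adjacent). The SAP gives neither the exact start points nor the variance ratio. The 80% is therefore attainable for one test of one measure, but it can be neither reproduced uniquely nor called wrong. Under no effect, one test rejected in 4.7% to 5.6% of runs.

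**2. Critical value and shift.** The two-sided .05 critical value is 1.960. The shift that gives 80% power is 1.960 + 0.842 = 2.802.

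**3. Either task suffices, no true effect.** Two-sided error = 1 − P(|Z1| < 1.960 and |Z2| < 1.960). At r = 0 this is 1 − .95² = .0975. False improvement = 1 − P(Z1 < 1.960 and Z2 < 1.960). At r = 0 this is 1 − .975² = .0494.

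**4. Both tasks required, both respond.** Power = P(Z1 > 1.960 and Z2 > 1.960) with each mean 2.802. At r = 0 this is .80² = .64.

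| r (assumed) | Either: two-sided error | Either: false improvement | Both required: power |
|---|---|---|---|
| 0 | 9.75% | 4.9% | 64% |
| .5 | 9.1% | 4.5% | 69% |
| .9 | 7.0% | 3.5% | 75% |
| .99 | 5.7% | 2.8% | 78% |

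For one test the corresponding figures are 5%, 2.5% and 80%. The simulated randomization test gave 8.7% to 9.5% two-sided error for the either-task rule (error correlation between tasks 0 to .8), broadly in line with the table.

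**5. Only one task responds (hypothetical).** One mean is 2.802 and the other 0. The chance of concluding improvement is 80% to 81% if either suffices and 2.0% to 2.5% if both are required. On an average of the two it is Φ(1.401/√((1+r)/2) − 1.960), which falls from 51% at r = 0 to 29% at r = .99. With a named primary task it is 80% if that task is the responder and 2.5% if not.

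**6. What each simple reading gives.** One named task, or one defined combined score: error .05, and power 80% if the SAP's effect of 1.0 refers to that measure. Two tasks tested and reported separately: each result is valid at .05 for its own task.

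**The case for a change.** The strongest case for a change is that the omission is genuine and cheap to repair. A sentence naming the primary task or the combined score would remove the choice before results are seen, at no cost in data. The singular wording of the criterion suggests a single score, yet none is defined. The SAP cites the main proposal for describing the tasks, not for a decision rule, so it may not settle the matter. If the results split between tasks, the conclusion does depend on the rule.

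That the supplied text is silent stands, and so do the figures in the table. Three parts of the argument do not carry the weight placed on them:

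- The test is defined: procedure, software, reference distribution, sidedness and threshold are all stated, and the power paragraph refers to that test in a section whose only threshold is .05.
- The wide range in step 5 needs one task with exactly no effect. The Protocol also lists focused training in a specific /r/ context and broad training across all /r/ contexts, and ties neither to one outcome. Nothing shows that goodness judgment goes untrained.
- The d_2 point is one of reporting. No alpha or power attaches to d_2, and two values per child can both be shown.

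**Conclusion.** No change to the plan follows. The .05 and 80% are per-test figures; study-level error and power across two tasks are simply not stated. This is missing detail that an analyst can fill sensibly, by testing each task at .05 and reporting both, or by following whatever the main proposal specifies.

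The consequence for the trial's directional question is modest. Even under the loosest rule the chance of falsely concluding improvement stays at or below 4.9%, against 2.5% for one test; the 9.75% also counts false findings of worsening. Requiring both tasks would lower power to between 64% and 78%, but the SAP does not claim 80% for that rule. Nor does one remedy stand out: a primary task, a combined score, both required, or a Holm adjustment are trade-offs for the sponsor to weigh.

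A statement of which task or score is primary, and that the 80% refers to it, would be a helpful clarification. The sizes rest on the normal approximation, on 80% power holding for each task, and on assumed correlations of 0 to .99. The conclusion would be different if the documents claimed .05 or 80% for a rule that does not deliver it. They make no such claim.

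### Production of /r/ is claimed under the randomized multiple-baseline design, but it is analysed only by a pre-post effect size that ignores the randomized start

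*SAP*

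**What the plan says.** The Protocol's Objective covers both outcomes: "Evaluate whether online perceptual training improves perception and production of /r". Its Summary Statement says the study will test whether training "leads to measurable improvements in both perception and production of /r/ in children with RSE and atypical perception, using a robust, randomized multiple-baseline design".

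SAP section 4.3 treats the two outcomes differently.

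- **Perception.** Progress is "tracked continuously across baseline and treatment phases using percent accuracy on the two perceptual tasks", and the next sentence applies the randomization test to that accuracy. A per-child d_2 (baseline against maintenance) is added, to judge "whether the effect of treatment on perceptual accuracy exceeds 1.0".
- **Production.** There is one sentence: "The same effect size measure will be used to compare production accuracy in the first three baseline sessions versus the three post-treatment maintenance phases". Its stated purpose is to test for transfer from perception.

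The power paragraph of SAP 4.3 covers the randomization test only. Under Design and Procedures, the Protocol randomizes baseline length (4–10 sessions), followed by 12 treatment and 3 maintenance sessions. Production probes are stated for baseline ("Perception and production of /r/ are probed repeatedly without intervention") and for maintenance. The documents do not say whether production is also probed during treatment.

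**The concern.** In a multiple-baseline design, protection against untreated change comes from the staggered, randomized start of treatment. An effect should appear when treatment begins, at a different session for different children. The production contrast does not use this. It compares the opening three sessions with the closing three, whatever start was drawn, so improvement from maturation or repeated probing counts in full as transfer.

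The perception d_2 has the same weakness, but the randomization test stands beside it. The production d_2 stands alone, with no null distribution or error rate. A large value could be reported as randomized evidence that perceptual training improves speech, which the analysis cannot support.

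**Working it through.** **The plan's own figure.** The only calculated figure is 80% power for the randomization test (n = 10, effect 1.0, 15 observations, autocorrelation .25, at least 4 start points). Simulation gives .80–.82 with equal variances and starts spread over 4–10 or set at 4/6/8/10. It gives .64–.68 with four consecutive starts, and .48–.65 if the intervention SD is 1.5 times the baseline SD (assumed). The spacing and variance ratio are not stated, so 80% is reachable but neither confirmed nor refuted. It concerns perception, and this point does not depend on it.

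**Distance between the two production windows.** Let b be the baseline length and count one equally spaced slot per session (assumed). The first window is sessions 1–3, centre 2. The maintenance window is sessions b+13 to b+15, centre b+14. The gap is (b+14) − 2 = b+12, which is 16 sessions at b = 4 and 22 at b = 10. The random start changes only this gap. Untreated drift of 1/22 = .045 to 1/16 = .063 SD per session therefore yields a 1.0 SD difference with no treatment effect.

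**Noise in one child's d_2.** Per child, d_2 = (maintenance mean − baseline mean) / √((s₁² + s₂²)/2), with three sessions in each window. With independent errors and no drift, d_2 ≥ 1 is the event t ≥ √1.5 on 4 df, probability .144. At least one of ten children then reaches 1.0 with probability 1 − (1 − .144)¹⁰ = .79. At autocorrelation .25 the per-child figure is .200 by simulation.

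**Effect of drift.** The documents give no drift, so a range is assumed: linear drift, no treatment effect, SD 1, n = 10, b uniform on 4–10, 20,000 trials. Entries in the first three result columns are the percentage of trials in which group d_2 exceeds 1.0.

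| Drift (SD per session) | Mean of child d_2, autocorrelation .25 | Mean of child d_2, independent errors | One SD pooled over children, autocorrelation .25 | Children of 10 above 1.0, autocorrelation .25 | Start-point randomization test, rejection rate |
|---|---|---|---|---|---|
| 0 | 2.0% | 0.5% | 0.2% | 2.0 | 4.7% |
| .01 | 5.9% | 2.1% | 1.4% | 2.6 | 4.3% |
| .02 | 15.5% | 7.9% | 5.2% | 3.2 | 4.9% |
| .05 | 73.1% | 65.8% | 56.3% | 5.4 | 5.7% |

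At autocorrelation .25 the average group mean d_2 is .00, .27, .53 and 1.32 at the four drifts. The 2.0 children at zero drift reflect three-session noise, not drift.

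The last column assumes independent starts on 4–10, the mean after minus the mean before treatment start, a p-value on absolute values, 999 permutations, 3,000 trials and autocorrelation .25.

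**Power of that test if used for production** (same set-up, zero drift):

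- Abrupt 1 SD step at treatment start: 76%.
- Linear build to 1 SD: 7–11% across runs.
- Step six sessions late: 2–3% with no lag; 76% with a matching six-session lag and the maintenance sessions included.

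**The case against.** The Summary Statement is one sentence about the study as a whole and assigns no test to either outcome. The SAP, which governs analysis, openly gives production a different measure and never calls it randomized evidence. The 1.0 benchmark is worded for perceptual accuracy, so production has no success rule and strictly no false-positive rate. The drift is assumed: .05 SD per session means .05 × 16 = 0.8 to .05 × 22 = 1.1 SD of untreated gain, which at three sessions a week throughout (assumed) takes about 5 to 7 weeks. Entry requires established errors ("Must have persistent speech errors specifically affecting the English rhotic /r/ sound"), which points to low drift. Repeated baseline probes would show drift. Transfer may lag, so comparing before training with after it is reasonable, and the alternative test is weak for gradual transfer. The main proposal, which the SAP cites, may say more.

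Much of this stands. The upper drift is unsupported, and at 0–.01 SD per session the group rate is only 0.2–6% across the variants above. Carrying over 1.0 is a reading, suggested by the SAP's use of the same measure and by its power paragraph treating 1.0 as the smallest effect that matters clinically. The power limits are real.

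The central point remains. The SAP calls the production contrast a test of transfer, and the Protocol names the randomized design when it claims both outcomes, yet the contrast does not use the randomization. Baseline probes could reveal drift, but no such use is prespecified for production. The wording of the randomization-test sentence does not mention production, and the sentence before it defines accuracy by the perceptual tasks. Blinded listeners guard against rating bias, not maturation or practice.

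**Conclusion.** The concern holds and should be fixed. Followed as written, the plan yields randomized evidence for perception and an uncontrolled pre-post change for production, although the Protocol claims both under the randomized design. This follows from the text and needs no drift value.

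The size of the consequence is less certain. It depends on assumed linear drift, equal session spacing and the unstated carry-over of 1.0. On those assumptions the artefact is modest at the low drift that the entry criteria favour and large only at the unsupported upper end. The powered perception analysis is not affected.

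**What to change.** In SAP 4.3, describe the production d_2 as uncontrolled pre-post change that cannot by itself establish transfer, and say whether 1.0 applies to it. In the Protocol's Summary Statement, credit the randomized design with testing perception only and list production as a descriptive pre-post outcome. This costs only wording and a weaker production claim.

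If production is also probed during treatment, a better course is to prespecify the same start-point randomization test for production as a secondary analysis. Fix any lag in advance, keep d_2 as descriptive, and state that a non-significant result is inconclusive, given the low power for gradual or unmatched delayed transfer. This costs one further run of a test already planned.
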